## **Promoting Self-Management of Breast and Nipple Pain with Biomarkers and Technology (PROMPT) for Breastfeeding Women study (1 R01 NR020041-01) RCT**

### **Purpose/Introduction:**

Every year, 1 million women cease breastfeeding (BF) before 6 months, the minimum time required for optimal maternal well-being and to promote their infant's health, physical growth, and development. The highest rate of BF cessation occurs within 3 weeks after delivery, with 30% of women ceasing BF due to acute breast and nipple pain (BNP). BNP is a complex and understudied biobehavioral phenomenon involving nociceptive signaling that stimulates multiple pathways - somatic (mechanical compression and cracked nipples), visceral (uterine cramping), and the autonomic nervous system (engorgement). Enhanced pain sensitivity, a physiologic pro-nociceptive state measured by somatosensory function and genomics, may increase women's sensitivity to BNP. Women who experience BNP beyond BF initiation report lower BF self-efficacy a key predictor of BF at 6 months, and increased symptoms of maternal distress (anxiety, depression, stress, and fatigue), which contribute to a greater risk of early BF cessation (< 3 weeks BF), decreased maternal well-being, and low maternal self-efficacy to care for their infant. Thus, a critical gap exists in identifying effective biobehavioral self-management interventions for women during BF initiation to manage BNP, increase BF self-efficacy, BF duration and decrease symptoms of maternal distress.

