**Justification of Sample Size:**

The sample size objective for the study is to recruit  $N = 280$  women who will be randomly assigned to the *BSM* or attention control study groups at a 1:1 ratio (140 per group). This objective provides 80% power ( $\alpha = 0.05$ , two-sided) to detect a standardized mean difference (Cohen's  $d$ ) of 0.39 or more between the *BSM* and attention control groups. It also provides 80% power to detect an odds ratio of 2.5 or more in exclusive BF between the two groups, assuming that the exclusive BF rate of the control group will be 10% higher than the national population rate in 2017 at 6, 9, 12, 18, and 24 weeks. These calculations account for "loss to follow-up" as high as 25% at 24 weeks, despite the substantially lower attrition (6%) in our pilot study. Based on our pilot study, we approached 78 women to meet our sample size of 60, with a failed screening rate of 25%. Thus, we intend to approach 374 women, which is 25% higher than our proposed study sample to meet our sample size. We anticipate that approximately 70% of the study sample will be WAHS or HHC patients.

In the pilot study, RM-ANCOVAs (with the baseline value of a measure as the covariate) revealed standardized mean differences larger than  $d = 0.39$  for the "main effect" of the intervention on BNP intensity ( $d = 0.45$ ), pain severity ( $d = 0.60$ ), cumulative pain ( $d = 0.64$ ), and BF self-efficacy ( $d = 0.48$ ) across the 1-, 2-, and 6-week time points. For BNP interference, the value of  $d$  was 0.39 at week 1, but smaller at weeks 2 and 6. Furthermore, the odds of exclusive BF in the intervention group are 2.9 times higher than the control group at 6 weeks, which is also higher than the hypothesized OR = 2.5. Therefore, we are confident that the sample size goal will be sufficiently powered to detect intervention effects on key variables for SA1 and SA2. Finally, the sample size estimate does not reflect our plans to conduct analyses based on repeated measurement of outcome variables at the 1, 2, 3, 6, 9-, 12-, 18-, and 24-week time points (due to the dearth of information regarding 24-week outcomes). Generally, the inclusion of data for an outcome variable across additional time points marginally enhances statistical power, especially for testing "main" and "interaction" effects of intervention and time.

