### IFSMT Proximal Outcomes.

#### Individual & Family Self-Management Behaviors.

**Acute BNP.** A visual analogue scale (0 - 100) used to measure BNP intensity during the last BF. Acute BNP will be measured with the short version of the Brief Pain Inventory. The Inventory has good reliability and validity with BNP. The Inventory has two subscales: pain intensity (4 items) and pain interference (7 items) and collects data on use of analgesics and of non-pharmacological measures. For initial data analysis, the average pain intensity and interference scores will be used, and other measures will be quantified. The McGill Pain Questionnaire short form is a reliable self-report measure of pain perception. It entails 15 verbal descriptors of sensory and affective dimensions of pain and is scored on a 4-point scale (0-none to 3-severe). Higher scores indicate higher levels of sensory and affective components of pain (range 0-45). Internal consistency reliability is in the excellent range for total pain score (Cronbach's alpha = 0.96).

**Cumulative BNP.** A score of acute BNP pain intensity from the VAS (0 - 100) at baseline, 1, 2, 3, 6, 9, 18, and 24 weeks will incrementally (baseline + 1 week, baseline + 1 and 2 weeks, etc.) be added together.

**NINR PROMIS Scales for Maternal Well-Being Symptoms.** The PROMIS scales of anxiety, perceived stress scale, sleep and fatigue. All PROMIS measures are based on the T-score (mean = 50, standard deviation = 10). In most cases 50 equals the mean in the U.S. general population.

**Edinburgh Postnatal Depression Scale.** Postnatal clinical screening tool for depressive symptoms with any score >10 indicates risk for depression and scores > 13 a depressive illness that requires referral. Women will be referred to their provider for fourth trimester care and may continue in the study. The scale has a sensitivity of 85%, specificity of 77% to identify women at high-risk for depression.

**H&H Lactation Survey.** A 20-item questionnaire maternal perception of milk supply with a 7-point Likert scale from 1 (strongly disagree) to 7 (strongly agree). Total scores ranged 20 ~ 140, with higher scores representing a higher perceived milk supply. The satiety subscale correlates with insufficient milk supply.

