**SA1.** Initially, mixed effects linear modeling will be applied to contrast mean levels of pain at the 1-, 2-, and 3-week time points. The analyses will be repeated for a series of pain outcome measures, including BNP intensity, BNP interference, and cumulative BNP. The models will include “main” effects for intervention and time, an interaction between intervention and time, a random effect for “subject”, and the baseline value of the dependent variable as a covariate. Modeling results will be used to test for a time-by-intervention interaction. If the interaction is non-significant, the model will be re-fitted without it and testing will focus on the main effect of intervention. Regression diagnostics will be applied to all models to identify non-normality in residuals and potentially biasing effects of outlying observations. While mixed effects linear models are resistant to the impact of limited amounts of missing data, we will also utilize multiple imputation methods, as described below, to evaluate the sensitivity of model estimates and testing results to missing observations. Following evaluation of intervention effects at the 1-, 2-, and 3-week time points, we will proceed to assess differences in acute and cumulative BNP intensity and interference at 6, 9, 12, 18 and 24 weeks. Additionally, we will investigate whether subject-level “trends” or “growth curves” in pain levels across all eight study time points differ between the intervention and control conditions. If necessary, demographic variables will be included in the regression models both to account for potential confounding effects that might arise via imperfect randomization and to reduce unexplained between-subject variation in outcome variables.

**SA2. H2A.** We will start by investigating the intervention's effect on proportion of exclusive BF after week 6. Initially, the Pearson Chi-square test will be performed to detect the difference between intervention and control groups at 6, 9, 12, 18, and 24 weeks, respectively. Furthermore, a generalized linear mixed model with a logistic link will be applied to analyze the “main effect” of intervention and time, and “interaction effect” of intervention by time. The procedure to fit and re-fit the model will be similar to the approach for pain measures in SA1. The measure for BF self-efficacy, yield scale scores

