which range from 14-70. We will treat BF self-efficacy scores as "continuous" variable and follow the approach in SA1 to investigate the intervention effect on BF self-efficacy over time. **H2B.** Subsequently, we will assess intervention effects on maternal well-being - anxiety, depressive symptoms, fatigue, stress, and sleep disturbance over all the time points. Each of these variables' measurement scores will be treated as "continuous" and effects of the *BSM* intervention will be investigated following a similar approach as for the pain measures in SA1. Because these variables are highly interrelated, we will evaluate their response to intervention effects simultaneously. In this approach, differences in the quadrivariate means of these variables between the *BSM* and attention groups will be analyzed using multivariate mixed effects linear modeling in an approach analogous to that for the pain measures in SA1 but with the inclusion of covariances between random intercepts for the anxiety, depressive symptom, fatigue, and sleep disturbance scores at the subject level. Across the modeling procedures related to SA2, regression diagnostics will be applied to investigate suitability of distributional assumptions and potential biasing effects of outliers.

**SA3.** We will model effects of pain sensitivity SNPs on quantitative sensory testing measures, BNP intensity and interference, BF outcomes in SA2, and maternal and pain self-efficacy across all the time points. In addition, we will also assess the effects of individual quantitative sensory testing measures on all the outcome measures aforementioned over time. Analyses will utilize "linear/generalized linear" modeling with univariate and multivariate dependent variables, will account for correct temporal ordering among time varying measures, and will evaluate correlations between measures that jointly vary in time in response to other factors/covariates.

We have planned for attrition rates as high as 25%. However, our goal is to minimize attrition by instituting a participant outreach plan –namely, contacting participants to complete modules, providing monthly updates regarding child development, and encouraging women to remain involved. In statistical analyses, we will follow each model based only on "observed data" with sensitivity analyses in which Markov Chain Monte Carlo multiple imputation is used to assess the possibility and impact of "missing at random" data.

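### For the mixed-model outcomes, including primary pain at weeks 1-3, the only missing-data sensitivity analysis assumes missing at random, as the model itself does, so it says little about loss that depends on unrecorded pain

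*Combined protocol and SAP*

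**What the plan says.** Under SA1 in Data Analysis and Management, pain at weeks 1, 2 and 3 is compared with a mixed effects linear model: intervention, time, their interaction, a random subject effect and the baseline value. The section calls such models resistant to limited missing data and adds that "we will also utilize multiple imputation methods, as described below, to evaluate the sensitivity of model estimates and testing results to missing observations".

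The description that this points to is in the attrition paragraph after SA3. Each observed-data model is followed by "sensitivity analyses in which Markov Chain Monte Carlo multiple imputation is used to assess the possibility and impact of" data missing at random. No delta-adjusted, tipping-point, pattern-mixture or reference-based analysis appears anywhere, and the imputation variables are not listed.

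Five other places bear on the point:
- Justification of Sample Size allows for up to 25% loss at 24 weeks and cites 6% attrition in the pilot.
- Significance puts the rise in the risk of stopping at 10-26% for each day that pain continues.
- Participant Population expects more women in the BSM arm to keep breastfeeding.
- Under IFSMT Proximal Outcomes, the pain VAS is "used to measure BNP intensity during the last BF".
- Post Enrollment Exclusion Criteria removes a woman after three consecutive missed data points or at her own request. It also lists failure to log daily entries as non-compliance that may lead to withdrawal. Stopping breastfeeding is not listed.

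**The concern.** A sensitivity analysis should change the assumption that is in doubt. Here the doubtful assumption is that, given the recorded data, non-response does not depend on the pain that went unrecorded. Both the mixed model and the planned imputation make it. Imputation under MAR cannot assess whether MAR is true.

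The protocol's own rationale makes the assumption questionable. The introduction says that stopping peaks within three weeks of delivery, "with 30% of women ceasing BF due to acute breast and nipple pain", and H1 is tested in those same weeks. A woman whose pain worsens between two surveys may stop answering before the worse score is captured. If this happens more in one arm, the arm difference is biased, and agreement between model and imputation could be reported as robustness when it shows nothing of the kind.

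Loss could also differ in the other direction. Table 1 asks only the BSM arm for daily log entries in the first six weeks, so withdrawal for not logging falls mainly on that arm.

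**Working it through.** **1. The plan's own figure.** Inputs from Justification of Sample Size: d = 0.39, two-sided alpha 0.05, 80% power, 25% loss, 140 per group.

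- n per arm = 2(1.960 + 0.842)² / 0.39² = 103.2, rounded up to 104.
- Allowing for loss: 104 / 0.75 = 138.7, rounded up to 139 per arm, total 278 against 280 stated. The figure reproduces.
- 140 × 0.75 = 105 completers per arm give 80.7% power (normal approximation) or 80.3% (t-test).

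The 25% allowance therefore protects precision. It does nothing about bias.

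**2. Possible shift in the pain difference.** None of these inputs is in the documents. Assume missing shares p_C = 20-30% (control) and p_B = 10-20% (BSM), unseen pain δ = 10-20 VAS points above the MAR prediction in both arms, and SD 25.

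Shift = (p_C − p_B) × δ

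- Smallest: (0.20 − 0.20) × 10 = 0 points.
- Largest: (0.30 − 0.10) × 20 = 4 points; 4/25 = 0.16 SD; 0.16/0.39 = 41% of the design effect.
- Like ends paired (gap 0.10): 1 to 2 points, 0.04 to 0.08 SD, or 10% to 21%.

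MAR analysis puts both arm means too low, control by more, so the BSM benefit is understated. If δ differs by arm, the range widens and the sign can change.

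**3. Does the planned check notice?** Simulation under assumed settings: within-woman correlation 0.5, true d = 0.39, about 25% dropout by week 3, log-odds of dropout 1 per SD of pain, 6,000 per arm, 4 replicates. The imputation was sequential regression within arm on baseline and earlier scores. This makes the same MAR assumption as MCMC and uses the same variables as the mixed model. Week-3 effect in SD units:

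| Dropout depends on | Full data | Mixed model | MAR imputation |
|---|---|---|---|
| Previous recorded pain | −0.409 | −0.412 | −0.409 |
| Current unrecorded pain, both arms | −0.401 | −0.363 | −0.361 |
| Current unrecorded pain, control only | −0.384 | −0.284 | −0.281 |

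The two analyses never differ by more than 0.003. In the second row the mixed model loses (0.401 − 0.363)/0.401 = 9.5% of the effect; in the third, (0.384 − 0.284)/0.384 = 26.0%.

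**4. What a tipping-point analysis would report.** Take an MAR estimate of 0.39 and the same missing share f in both arms. Significance is lost when f × (δ_B − δ_C) = 0.39 − critical d, with δ in SD units.

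- f = 25%: critical d = 1.96 × √(2/105) = 0.271; (0.390 − 0.271)/0.25 = 0.48 SD.
- f = 6%: 131.6 per arm; critical d = 0.242; (0.390 − 0.242)/0.06 = about 2.5 SD.

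This requires unseen BSM pain to exceed its prediction by more than unseen control pain does. In the opposite direction, suppose the true effect is 0.39, 25% are missing, and only control pain is shifted. Shifts of 0.25 and 0.50 SD attenuate the estimate by 0.0625 and 0.125, and power with 105 per arm falls to 66% and 48%. At 6% missing, shifts of 0.25 to 1.00 SD move the effect by only 0.015 to 0.06 SD.

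**The case against.** The strongest reply is that stopping breastfeeding is not missingness. No withdrawal rule mentions it, and Table 1 schedules the pain scales for both groups at every assessment with no exemption. Because the VAS concerns the last feed, a woman who has stopped could still report it, and her score might capture the pain that made her stop. This stands. A reader might infer that every woman who stops becomes a missing pain score; the documents do not say so. Nor would adding points to the pain of a feed that never took place have a clear meaning.

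A reader might also infer that model and imputation must agree whatever the truth. That holds only if both use the same variables. The imputation could draw on breastfeeding status, the other pain scales or self-efficacy, and then differ. If dropout depends only on recorded pain, MAR holds and both analyses are unbiased, as the first row of the table shows. The plan neither names auxiliaries nor offers a way to tell which case applies.

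Two further points stand. The first H2A analysis, chi-square tests on observed cases, is not a mixed model. There MAR imputation does relax an assumption and is a legitimate check. And the missing shares assumed above average 15-25% across arms. In the pilot, 87% were still breastfeeding at six weeks, so about 13% had stopped, and attrition was 6%. The planned 25% is a ceiling for 24 weeks, so applying it to weeks 1-3 is a worst case.

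None of this supplies an analysis that departs from MAR for the primary outcome.

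**Conclusion.** The point holds for the mixed-model outcomes, including primary pain at weeks 1-3. Their only missing-data sensitivity analysis shares the main model's assumption. With the same variables, agreement between the two gives no reassurance about non-response driven by unrecorded pain.

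The absence of any other analysis is certain from the text. The amount of bias is not: 0-4 points is a range under stated assumptions, it includes zero, and it would be small at the pilot's attrition. A reader might infer that the plan risks a false claim of benefit. The scenario the protocol itself suggests, with more control scores missing and those scores higher than predicted, biases toward the null and costs power instead. The reverse cannot be excluded, but nothing in the documents makes it the expected case. This is a cheap improvement to the plan and does not show that the primary analysis is invalid.

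**What to change.** 1. Keep the MAR imputation, including for the H2A chi-square tests. List its variables, and include breastfeeding status and the other pain scales as auxiliaries.
2. Prespecify a delta-adjusted tipping-point analysis for pain scores missing through non-response. Vary delta separately by arm, and report the values at which the weeks 1-3 conclusion changes.
3. Do not describe the MAR imputation alone as evidence of robustness to missing data.
4. State separately how the VAS is scored, or what quantity is being estimated, once a woman has stopped breastfeeding. Do not delta-impute those scores as if they were ordinary missing data.

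The cost is some wording in the analysis section and extra imputation runs, with no new data, visits or participants. The delta grid should be fixed before any unblinded comparison, since a range chosen afterwards would carry little weight.

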**BNP leads to BF cessation.** Clinically, BNP during BF initiation is managed as a "normal" phenomenon that women experience. For women who experience unresolved BNP during BF, BNP triggers a complex feedback loop which creates a challenging situation that includes stimulation from the glandular, somatic, and visceral tissues, which is transmitted via nociceptors pathways. During the critical **2-3 weeks of BF**, women will continue BF with BNP, to provide optimal nutrition and build their maternal self-efficacy, detrimentally, for each day of ongoing BNP, the risk of BF cessation increases by 10-26%. Common triggers of BNP are related to anatomic factors, such as abnormal nipple shape, pumping, and ankyloglossia, or an infectious process. These triggers may be resolved with guided BF interventions and treatment. However, without resolution, 30% of women (1 million) cease BF early due *ongoing BNP* which disrupts the neurohormonal cascade of lactation triggering *inadequate milk volume* and a *lack of*

*infant satiation.* At 1 and 3 months, 20 – 30% and 16% of women, respectively, experience ongoing pain even with professional lactation intervention. The persistence of pain without medical conditions or anatomic anomalies suggests a genetic risk of pain sensitivity and insufficient milk supply. A **genetic risk of enhanced pain sensitivity** may be used to identify women at high-risk for pain-related BF cessation and target precision interventions for BNP and also be a pathway to identifying women at risk for chronic pain due to a pain sensitivity phenotype.

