**Candidate pain sensitivity SNPs genotyping.** Blood and/or buccal cell samples will be collected at baseline before discharge. Blood will be drawn by trained hospital staff or members of the research team before discharge in the patient's hospital room. At the 6 week and 24 week follow up, blood will be drawn at HH in the lactation room. At the follow up appointments at WAHS, the PROMPT research team member will escort participant to the phlebotomy area. At UCHC, the blood will be drawn at UConn Health BBL or Clinical Research Center. The research team will endeavor to have the blood drawn during routine clinical blood draws. Samples will be transported to the School of Nursing Biobehavioral lab, UConn lab service center or [name] lab to be processed, and split, volume permitting, for liquid N2 storage of a white-blood-cell pellet for later RNA studies. DNA will be isolated using the Qiagen DNA Easy Kit and QC'd prior to delivery of 500 ng to the lab service centers at the University of Connecticut, such as Center for Genome Innovation (CGI), Microbial Analysis, Resources and Services (MARS) or the School of Nursing Associated Laboratories. Samples will be batched in groups of 10 for processing on The Illumina Methylation EPIC Bead Chip.

For buccal cell swabs, participants will be instructed to rinse their mouth with clean water and roll the sterile buccal brush firmly on the inside of both cheeks. The participant will roll one brush for 60 seconds on the first cheek and repeat again on the second cheek. Samples will be transported to the SON biobehavioral lab and stored at -80°C until processing in batches at a UConn lab service center or shipped to [name] lab for verification of results. Genomic DNA (gDNA) will be isolated from buccal samples using the OMNIgene•ORAL OMR-110). The samples are stable at room temperature for 30 days, allowing transport to the SON biobehavioral lab, UConn lab service center, and/or

Time Points Module	Item#	α	T1	T2	T3	T4	T5	T6	T7	T8	T9
Context factors:											
Breastfeeding Specific Factors  Module – FBF	48	N/A	X X								
Pain Coping Strategies  Module – DB, GI, C, S	27	0.80- 0.88	X X	X XX	X X	X X	X X	X X	X X	X X	X X
Quantitative Sensory Testing 	13	0.94	X				X				X
Process factors:											
Self-efficacy Scale  Module – DB, GI, C, PN-BF, S,	6	0.91	X X	X XXX	X X	X X	X X	X X	X X	X X	X X

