**Statistical analysis of methylation sequencing data.** Post-alignment analysis will be performed by using the MethPipe package (<http://smithlabresearch.org/software/methpipe/>). First, aligned sequences will be converted to MethPipe format using the to-mr command. Methylation levels and coverage for each symmetric CpG site will be calculated. Average CpG methylation levels of annotated genomic regions, i.e., promoters, exons, repeats, CpG islands/shores/shelves (CGI) will be calculated with the MethPipe roimethstat program. Only high-confidence genomic regions with at least 40 CpG observations from reads in the region will be retained for further analyses. Coordinates of promoters (-1000 bp and +100 bp from the transcription start site (TSS)), exons, introns and intergenic regions will be retrieved from Ensembl Regulatory Build (Ensembl release 101) and CGI annotations obtained from the UCSC Table Browser. Tissue-specific enhancer coordinates (+/- 1000 bp from peak) will be retrieved from the Human Encode Project38 (GRCh38/hg38). Hypermethylated regions and hypomethylated regions will be calculated by the hmr command from the MethPipe package. Unsupervised hierarchical clustering of 2 kb tile methylation will be performed using the R hclust command with the "ward" method. Correlation matrix will be calculated by the R corrplot package. Profile plot will be created by the R seqplots package. Gene ontology analysis will be performed by GREAT and DAVID Bioinformatics Resource 6.8. A Univariate ANOVA, followed by post-hoc Tukey HSD will be carried out to compare methylation within promoter region CGI for the six candidate genes (*OXTR*, *COMT*) identified in the preliminary studies. CGI methylation status of each gene will be assessed individually with control for multiple comparisons between conditions maintained, and post-hoc analysis with Tukey HSD will be adjusted to maintain an overall  $\alpha = 0.05$ .

**SA4.** We will model effects of DNA methylation of *OXTR* and promoter regions of *PRLR* haplotypes for different single nucleotides polymorphisms (SNPs) on BNP and maternal perception of lactation insufficiency, BNP intensity and interference, and BF frequency across all the time points. [name], will consult with the Institute for Systems Genomics to assist with statistical data analysis and interpretation of EPIC array raw data.

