EPIC array raw data will be imported into the statistical analysis software Partek® Genomics Suite® for normalization, quality control, differential analysis and biological interpretations (gene ontology and/or pathway analysis). Statistical calculations (available within the software) will include Logistic Regression, Chi Square, False Discovery Rate, Fisher Exact, Power Analysis, and ANOVA. We propose to use the significance threshold of  $P < 9 \times 10^{-8}$  to control the false positive rate for EPIC array DNA methylation studies.

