### **Inclusion/Exclusion Criteria:**

#### **Inclusion Criteria**

- female
- 18 - 45 years of age
- Patient at HH, WAHS, UConn Health
- given birth < 48 hours to a singleton infant > 37 weeks gestational age
- having intention to BF
- provided standardized BF basics during their antenatal care
- with access to the internet via own smartphone, other device, or study-provided smartphone (provided at baseline and returned at 6-month research visit)
- willing/able to consent to participate
- having ability to read and write English as the intervention has not been tested in Spanish speaking population.
- assessed by a lactation consultant (CLC/IBCLC) during BF before discharge

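### The exploratory methylation analyses specify no adjustment for cell composition or tissue, so associations with pain or milk supply may partly reflect cell mix

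*Combined protocol and SAP*

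**What the plan says.** All places are in the combined protocol and SAP.

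- **Sequencing** (Statistical analysis of methylation sequencing data): a univariate ANOVA with post-hoc Tukey HSD "will be carried out to compare methylation within promoter region CGI", with overall alpha held at 0.05. It has one factor and no covariate.
- **SA4** (same section): OXTR and PRLR methylation is modelled against BNP, perceived lactation insufficiency and breastfeeding frequency. No covariate or significance threshold is given in that description.
- **EPIC array** (end of SA4): the raw data are imported "for normalization, quality control, differential analysis and biological interpretations (gene ontology and/or pathway analysis", followed by a list of general tests and a threshold of P < 9 x 10^-8.
- **Samples** (Candidate pain sensitivity SNPs genotyping): blood, buccal cells or both are collected. On the array, "Samples will be batched in groups of 10 for processing on The Illumina Methylation EPIC Bead Chip". The only white-cell material mentioned is a stored pellet, kept for later RNA work.
- **Timing:** women enter having "given birth < 48 hours to a singleton infant". Samples are taken at baseline before discharge and again at 6 and 24 weeks.
- **Sequenced subset** (Whole Genome Methylation Sequencing): 40 women, made up of 5 with zero pain and 15 with the highest pain in each arm.
- **Infection:** Significance lists anatomic factors "or an infectious process" among the common triggers of BNP. Protection against Risk also foresees mastitis.

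The documents do not mention cell counts, estimated cell fractions, deconvolution or a tissue term.

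**The concern.** A methylation value from blood or a cheek swab is the mean over the cell types in the sample, weighted by their shares. If cell types differ in methylation at a tested region, and their shares differ along the contrast being tested, a difference appears although no cell has changed.

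This design gives cell mix several ways to vary. Two tissues are allowed. Visits run from the immediate postpartum period to 24 weeks. The sequenced women are chosen for extreme pain, and the protocol itself links infection to pain. Restricting an analysis to blood would remove the tissue problem but not the variation in white-cell shares within blood.

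What is at stake is the interpretation of SA3 and SA4. A reported link between methylation and pain or milk supply could be read as gene regulation when it is partly cell composition. Multiplicity control does not address this, because it limits chance findings and not bias.

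**Working it through.** **1. The plan's own figure.** The only stated sample size is for the whole trial: "This objective provides 80% power" for a standardized difference "of 0.39 or more between the *BSM* and attention control groups", "at a 1:1 ratio (140 per group"), with 25% loss.

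n per arm = 2(1.96 + 0.842)^2 / 0.39^2 = 103.2, so 104. Then 104 / 0.75 = 138.7, so 139 per arm, or 278 in total. This agrees with the stated 280. No power or sample size is given for the methylation analyses, so the rest is a range under assumptions.

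**2. Size of an artefact.** Apparent difference = (methylation gap between cell types) x (shift in cell share). For an assumed 10-point shift in share:

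- gap of 5 points: 5 x 0.10 = 0.5 points
- gap of 10 points: 1 point
- gap of 20 points: 2 points
- gap of 40 points: 4 points
- gap of 0: no artefact

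The documents give neither gaps nor shifts.

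**3. Chance that it is declared significant.** From the plan: 2 x 15 = 30 highest-pain and 2 x 5 = 10 zero-pain women. Assumed: between-woman SD of 5 points. Standard error = 5 x sqrt(1/30 + 1/10) = 1.826 points. Noncentrality = artefact / 1.826, with 38 degrees of freedom. The two-sided critical t is 2.024 at alpha 0.05 and 6.585 at 9 x 10^-8.

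| Artefact (points) | Noncentrality | Alpha 0.05 | P < 9 x 10^-8 |
|---|---|---|---|
| 0.5 | 0.274 | 5.8% | below 0.0001% |
| 1 | 0.548 | 8.3% | below 0.0001% |
| 2 | 1.095 | 18.7% | 0.0005% |
| 4 | 2.191 | 57.0% | 0.02% |

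**4. Sensitivity to the SD.** With an SD of 3 points, the alpha 0.05 rates are 7%, 14%, 43% and 94.5%. At the EPIC threshold, 2 points passes below 0.1% of the time, 4 points about 1%, and 8 points 73%.

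**5. Does adjustment work?** A simulation used 30 versus 10 women, no true methylation effect, a cell-share SD of 8 points and a residual SD of 2 points. With a 20-point gap between cell types and shifts of 5, 10 and 20 points, the unadjusted false-positive rate was 17%, 54% and 99%. With cell share as a covariate it was 4.6% to 5.2% in every scenario run. With no shift or no gap, both analyses stayed near 5%. The simulation adjusts for the true share, so estimated shares would leave some residual bias.

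**6. Limits of these figures.** They describe a single two-group contrast. Tukey adjustment over more than two conditions would lower them. They do not transfer directly to the SA4 models, where methylation is a predictor.

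**The case against.** Most of the case against concerns how far the point can be pushed, and much of it stands.

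- **A false link is certain.** A reader might infer this from the missing term. The documents do not support it. Bias needs cell-type-dependent methylation at the tested regions and a cell mix that differs along the tested contrast, and they give data on neither. With gaps of 5 or 10 points and a 10-point shift, the error rate is close to nominal.
- **The array step carries the same risk.** It does not at its stated threshold, with about 40 women and artefacts of up to 4 points. The number of women on the array is not stated, and a larger sample would raise the rate.
- **The postpartum shift alone confounds the pain comparison.** It does not. A shift shared by all women affects comparisons between visits, not a same-visit comparison of pain groups. For a paired baseline to week 6 change in 40 women (SD of change 5), a 2-point artefact would be significant 69% of the time at alpha 0.05. The plan specifies no such paired test.
- **The high-pain group contains the infected women.** The protocol names infection as a trigger but gives no infection rate at the sampling visits. It also says that triggers may be resolved.
- **COMT is tied to milk supply.** COMT is in the sequencing ANOVA; the SA4 methylation model names OXTR and PRLR.
- **The array may use blood only.** Its sentence follows the blood-handling text, and the SA4 aim names blood. That narrows the tissue question for the array but leaves white-cell mix open.
- **The details may be elsewhere.** The sub-study attachments were not available, specialist consultation on the array is planned, and SA3 allows unspecified covariates. None of this text specifies a cell-mix term.
- **Adjustment can change the question.** If immune change is part of the pain process, adjusted and unadjusted estimates answer different questions. This is a reason to report both.

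**Conclusion.** The point holds as a gap in exploratory analyses. As written, the sequencing ANOVA, the SA4 models and the EPIC analysis adjust for neither cell composition nor tissue, and associations with pain or milk supply may partly reflect cell mix.

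The exposure is mainly in the alpha 0.05 ANOVA, at the rates tabulated above, and in the SA4 models, which state no separate threshold. These rates depend on the assumed SD, gaps and shifts, and they fall to the nominal 5% if either gap or shift is zero. SA3 and SA4 are worded as exploratory, so a reader should not infer that the primary pain outcome or the SA2 outcomes are affected. The change should be made before methylation data are analysed.

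**What to change.** - Use one tissue for each methylation analysis, or add a tissue term.
- Replace the univariate ANOVA with a linear model that includes cell fractions, or their first one or two components when n = 40.
- Estimate the fractions with a reference-based method suited to the tissue, from EPIC data where a woman has them, or otherwise by deconvolution of the sequencing reads. The documents do not say that the sequenced women also have array data, so both routes need to be written down.
- Put the same terms in the EPIC and SA4 models, with a visit term wherever visits are pooled.
- Report unadjusted results alongside as a sensitivity analysis.
- If the sub-study attachments already specify this, cite them in the main plan.

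Cost: one to five degrees of freedom and some analysis time. No new samples are needed.
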